2.1 STUDY RATIONALE

Behavioral interventions have been successful in reducing and delaying diabetes by targeting weight loss through modifiable behaviors (e.g., diet and exercise). There remain significant difficulties implementing Diabetes Prevention Programs (DPP) in certain populations due to access and resource availability. The health disparities seen between individuals living in rural communities versus metropolitan areas are evident. Rural communities have a 17% higher rate of type 2 diabetes compared to their urban counterparts.

Previous efforts to culturally adapt the DPP for Hispanics are vital, yet critical gaps remain. Specifically, insufficient attention has been paid to Hispanics living in rural settings and the formidable barriers these individuals face. We intend to fill this gap. ISA Associates, in partnership with the Community Action Corporation of South Texas (CACOST), has developed a mobile web-based diabetes prevention program for Hispanic Americans living in rural communities. **STEPS: Small Changes to Prevent Diabetes** will be designed to increase knowledge and skills to help change lifestyle factors associated with diabetes of Hispanics living in rural settings. **STEPS** will also place a strong emphasis on Hispanic cultural beliefs and will include themes of *familismo*, Mexican inspired recipes, and community health workers (*promotoras*). **STEPS** will deliver culturally tailored information to users following assessments of their needs and personal situation. The program provides users with the information, skills, and tools needed to promote health and reduce risk for the development of diabetes. Materials will be multi-modal in format (e.g., narration by a program 'coach', culturally-appropriate visuals, graphics, interactive assessments with feedback, and tailoring of information). The goal of the program will be to promote self-management of diet and physical activity and minimize risks associated with diabetes.

We plan to test the effectiveness of **STEPS** in a randomized controlled trial with 165 Hispanic adults. Participants will be randomly assigned to receive either the mobile **STEPS** intervention or usual care. Before, about 3-months post randomization, and about 6-months post randomization, we will assess anthropometric data including height, weight, a1c; demographic data, diabetes risk and knowledge, dietary intake, and self-report PA.

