9.2 SAMPLE SIZE DETERMINATION

We examined power using treatment effects from two sources: 1) a meta-analysis examining the overall effectiveness of mobile device interventions on weight loss¹⁵⁴ and 2) a digital diabetes prevention program for low-income patients.⁸⁵ First, a meta-analysis examining the effects of mobile device interventions on weight loss found an average effect size of Cohen's d : 0.43 (95% CI:0.252-0.609; $p < 0.01$) across 11 mobile-based intervention studies.¹⁵⁴ This indicates an overall medium effect size. Second, Kim et al.⁸² developed and tested a mobile-based diabetes prevention program for a multi-racial/ethnic population. This study yielded a mean weight loss of 4.4% (SD 7.7%) at 12 months. This finding is associated with a Cohen's d =0.57, which is considered a medium effect size. To ensure our study is fully powered, we conducted our power analysis using the smaller effect size (Cohen's d =0.43) from Lyzwinski et al.¹⁵⁴, who examined the effects of mobile-based interventions on our primary outcome, participant weight loss.

We estimated power for the paired t-test for %weight loss (primary outcome). The G*Power 3.1 program¹⁵⁷ was used to determine that a Cohen's d of 0.43 and an α error probability of 0.05 requires a final sample size of 136 to be sufficiently powered ($1 - \beta$ error probability) at 0.80. Presuming a 20% attrition rate, randomizing a final sample size of 164 participants should be sufficient to detect significant differences in % weight loss across the two survey time points (i.e., at baseline and 3 months after the end of the intervention).

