9.4 STATISTICAL ANALYSES

9.4.1 GENERAL APPROACH

A paired t-test will be the main analytic technique for the primary measure (percent weight loss) and all continuous outcome measures. The test of the intervention effect will be the t-test for the

regression coefficient for condition, which will estimate the adjusted difference between the two conditions at posttest. That test will be two-tailed with a type I error rate of 5%. Chi-square tests will be used for all categorical outcome data.

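### Section 9.2's 20% attrition allowance is miscalculated: 164 randomised leaves about 131 completers rather than 136, and section 2.1 gives a different target of 165 (minor)

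*Combined protocol and SAP*

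**What the plan says.** Section 9.2 (Sample Size Determination) starts from "a Cohen's d of 0.43 and an α error probability of 0.05" and concludes that the trial "requires a final sample size of 136 to be sufficiently powered", with power of 0.80. It then adds the allowance for loss: "Presuming a 20% attrition rate, randomizing a final sample size of 164 participants should be sufficient". It names a paired t-test as the basis of the power calculation and does not say whether the test is one- or two-sided.

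Section 2.1 (Study Rationale) describes a "randomized controlled trial with 165 Hispanic adults". Nothing in the document reconciles 165 with 164.

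Three other sections bear on the point:

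- Section 7.2 says that people who withdraw after randomisation are not replaced, and that enrolment runs until the target sample size is reached. It does not give the number.
- Section 9.3 includes everyone randomised, plans imputation, and expects very little missing primary-outcome data.
- Section 9.4.1 tests the intervention effect through the regression coefficient for condition, two-tailed at 5%.

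**The concern.** An attrition allowance should make the number randomised large enough that the required number remain after the assumed loss. A reader can check in one line whether 164 does this, and at 20% loss it does not. The sentence is the plan's explicit claim that its sample size suffices, and it fails on the figures printed beside it.

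Two things are at stake. The first is whether the stated power matches the number of participants expected to provide a final weight. The second is when recruitment stops: section 7.2 relies on a single target, the protocol gives two, and later losses cannot be made good by replacement.

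**Working it through.** **Inputs.** From section 9.2: 136 required, 20% attrition, 164 randomised, d = 0.43, alpha 0.05, power 0.80. From section 2.1: 165. From section 9.4.1: a two-tailed between-condition test at 5%. Equal allocation is taken from section 6.3.

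**Reproducing 164.** Multiplying the requirement by one plus the attrition rate gives 136 × (1 + 0.20) = 163.2, which rounds up to 164. This applies the 20% to completers, not to those randomised.

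**Correct allowance.** Number randomised = required / (1 − attrition) = 136 / 0.80 = 170. Check: 170 × 0.80 = 136.

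**What the stated targets leave at 20% loss.**

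| Randomised | Expected completers | Shortfall from 136 | Attrition at which 136 remain |
|---|---|---|---|
| 164 (section 9.2) | 164 × 0.80 = 131.2 | 4.8 | 1 − 136/164 = 17.1% |
| 165 (section 2.1) | 165 × 0.80 = 132.0 | 4.0 | 1 − 136/165 = 17.6% |
| 170 (recomputed) | 170 × 0.80 = 136.0 | 0 | 20% |

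**Which test gives 136.** Power comes from the noncentral t distribution with n1 + n2 − 2 degrees of freedom and noncentrality d × √(n1·n2/(n1 + n2)). At d = 0.43, alpha 0.05 and power 0.80:

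- one-sided two-sample t-test: 68 per arm, 136 in total (power 0.802), an exact match;
- two-sided two-sample t-test: 86 per arm, 172 in total;
- paired t-test: 45 pairs two-sided, 35 one-sided.

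A one-sided two-sample calculation is therefore the likely origin of 136. That is an inference, because section 9.2 does not state it.

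**Power cost of the slip.** With 136 completers (68/68) the noncentrality is 0.43 × √34 = 2.507. With 131 (66/65) it is 0.43 × √(4290/131) = 2.461.

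| Test | Power at 136 | Power at 131 | Loss |
|---|---|---|---|
| One-sided two-sample (inferred) | 0.802 | 0.789 | 0.013 |
| Two-tailed between-arm (section 9.4.1) | 0.702 | 0.685 | 0.017 |

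**Splitting the two-tailed shortfall.** From 0.80 to 0.685 is 0.115. Of this, 0.80 − 0.702 = 0.098 comes from the base figure of 136, and 0.702 − 0.685 = 0.017 from the attrition arithmetic.

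**The case against.** The strongest reply is that this hardly matters. Five completers cost less than two points of power, and no estimate or test changes. Section 9.3 also keeps everyone randomised in the analysis, imputes missing values and expects very little missing primary data, while 164 already tolerates 17.1% loss. The point about size stands, and it is why this is a minor correction. The rest does not make 164 right under 20%. Section 9.2 itself adds an allowance to secure 136, and imputation does not restore the information in weights that were never measured. The expectation of little missing data makes the practical risk smaller, but it sits awkwardly beside a presumed 20% attrition.

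A second reply is that under the paired t-test named in section 9.2, 131 would be ample, since about 45 pairs suffice two-sided. That is true of that test, but it does not yield the printed 136 and is not the between-condition comparison of section 9.4.1. The shortfall here is measured against the plan's own stated requirement.

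Three stronger readings are tempting, and the documents do not support them:

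- A reader might take 0.685 as the price of the attrition slip. Most of the distance from 0.80 is already present at 136 completers and belongs to a separate problem.
- A reader might say that the plan adopted a one-sided basis. It states none, and section 9.4.1 is two-tailed.
- A reader might argue that 165, being odd, defeats the equal arms described in section 6.3. Randomly ordered blocks of 4 and 6 can stop mid-block at an even total too, and that section itself allows for modest imbalance during recruitment. A difference of one participant has no statistical weight.

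**Conclusion.** Wrong as written, and minor. Under the stated 20% attrition, 164 randomised leaves about 131 participants, not the 136 that section 9.2 requires. The figure that fits its own inputs is 170. The claim of sufficiency holds only if attrition is at most about 17%. The 165 in section 2.1 also falls short, at 132, and leaves section 7.2 without a single enrolment target.

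The slip by itself costs about five completers and 1.3 to 1.7 points of power. The completer counts rest only on printed figures. The power figures also assume d = 0.43, equal allocation and a two-sample t-test without covariate adjustment; the one-sided pair rests in addition on the inferred origin of 136.

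**What to change.** No increase in enrolment is needed. In section 9.2, do one of the following:

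- state that 164 randomised supports 136 completers only if attrition is at most about 17%; or
- keep 20% attrition and state about 131 expected completers.

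In either case, give the power for the planned two-tailed between-arm test at d = 0.43: about 0.70 at 136 completers, or about 0.69 at 131. Use one enrolment target in sections 2.1 and 9.2, so that section 7.2 refers to a single number. If the target becomes 165, the expected completers at 20% loss are 132.

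The cost is a change of wording and a less favourable stated power. Most of that drop comes from the base figure of 136, not from the attrition arithmetic. Randomising 170 would repair the arithmetic but would still leave power near 0.70 for the two-tailed test at 20% loss, so the base figure is best revisited in the same edit.

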9.3 POPULATIONS FOR ANALYSES

Because randomization carries the expectation of creating treatment groups equivalent with respect to known and unknown prognostic factors, removing randomized participants from the analysis runs the risk of tampering with this balance and introducing bias into the treatment comparisons. As a result, an intention-to-treat analytic approach will be followed such that all participants randomized into the study will be included in all analyses irrespective of protocol violations post randomization. Even with our best efforts, we can expect some missing data. For the primary outcome, missing data will be limited to cases where we are unable to receive a weight as per participant request. Because we allow participants to opt out of any biometric or question, there is the possibility that there is missing data for the primary outcome. However, very little missing data is anticipated. For secondary measures, missing data will consist of those who fail to complete the 3 or 6-month follow-up survey. We will conduct an initial evaluation of missingness by performing a series of logistic regression analyses where the indicator of missing data is the outcome and potential explanatory variables (e.g., condition, screening status, demographic characteristics) serve as predictors. We will then use imputation to manage missing data.

9.4 STATISTICAL ANALYSES

9.4.1 GENERAL APPROACH

A paired t-test will be the main analytic technique for the primary measure (percent weight loss) and all continuous outcome measures. The test of the intervention effect will be the t-test for the

regression coefficient for condition, which will estimate the adjusted difference between the two conditions at posttest. That test will be two-tailed with a type I error rate of 5%. Chi-square tests will be used for all categorical outcome data.

9.4.2 ANALYSIS OF THE PRIMARY ENDPOINT(S)

The primary outcome is percent weight loss, and secondary outcomes include: HbA1c levels, diabetes knowledge, dietary intake, and self-reported physical activity. All but the weight and HbA1C measures (assessed by the research coordinator) will be self-reports using established scales that have evidence of reliability (internal consistency and/or a test-retest reliability) and validity. A paired t-test will be the main analytic technique for the primary measure (percent weight loss) and all continuous outcome measures. The test of the intervention effect will be the t-test for the regression coefficient for condition, which will estimate the adjusted difference between the two conditions at posttest. That test will be two-tailed with a type I error rate of 5%. Chi-square tests will be used for all categorical outcome data. We will perform the analysis using SAS PROC GLM, Version 9.1.¹⁴⁸ We will perform these analyses in collaboration with our statistical consultant, [name].

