1.1 SYNOPSIS

Title:	Diabetes Prevention for Hispanics Residing in Rural Communities: A Mobile Web-based Approach
Grant Number:	R44MD014082
Study Description:	Two-arm, parallel-group randomized controlled trial comparing a tailored, mobile web app diabetes prevention program with usual care control to reduce diabetes risk by at 3 and 6 months among Hispanic adults who are at risk of developing Type II Diabetes.
Objectives*:	Objectives: Primary—evaluate the effect on percent weight loss . Secondary—evaluate effects on A1C, diabetes knowledge, eating patterns, and physical activity.
Endpoints*:	Endpoints: Primary—weight assessed at each study visit (baseline, 2 post visits). Secondary—validated scale scores at baseline and 2 follow-ups.
Study Population:	Hispanic adults aged 18+, with prediabetes, and smartphone owners in South Texas
Phase* or Stage:	Phase II clinical trial
Description of Sites/Facilities Enrolling Participants:	Single U.S. community health center in South Texas
Description of Study Intervention/Experimental Manipulation:	The study intervention includes a variety of education series with explanatory videos, interactive content, infographics, and engaging tools aimed at increasing diabetes risk knowledge, reducing risk behaviors, and improving overall health. Participants review the intervention across three months. Comparator: Usual care.
Study Duration*:	19 nb months
Participant Duration:	6 months

[figure not shown]

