9.1 STATISTICAL HYPOTHESES

- Primary Endpoint(s):

We hypothesize that, compared to participants who receive usual care, participants who receive the tailored mobile web-app, STEPS, will have a higher percentage of weight loss at 6 months post-randomization. Alternatively, our null hypothesis is that there will be no difference between arms in screening completion at 6 months.

- Secondary Endpoint(s):

A1C (3 and 6 months):

We hypothesize that the intervention arm will report a lower A1C at 3 and 6 months than the control arm; the null hypothesis is that there will be no difference between arms.

Diabetes Knowledge (3 and 6 months):

We hypothesize that the intervention arm will report higher diabetes knowledge (higher total score) at 3 and 6 months than the control arm; the null hypothesis is that there will be no difference between arms.

Eating Patterns (3 and 6 months):

We hypothesize that the intervention arm will report better eating patterns aligned with weight loss and management (total score) at 3 and 6 months than the control arm; the null hypothesis is that there will be no difference between arms.

Physical activity (3 and 6 months):

We hypothesize that the intervention arm will report higher amounts of physical activity at 3 and 6 months than the control arm; the null hypothesis is that there will be no difference between arms.

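### Sections 9.2 and 9.4 name a paired t-test, which cannot compare the randomised arms, and 9.4 then gives a different, between-arm test; one primary test should be stated

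*Combined protocol and SAP*

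**What the plan says.** The synopsis (1.1) describes the design as "Two-arm, parallel-group randomized controlled trial comparing a tailored, mobile web app diabetes prevention program with usual care control". Section 6.3 allocates individuals in permuted blocks, with no matching of participants across arms. The primary hypothesis in 9.1 is that STEPS participants "will have a higher percentage of weight loss at 6 months post-randomization", compared with usual care.

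On the analysis, 9.4.2 reads "A paired t-test will be the main analytic technique for the primary measure (percent weight loss) and all continuous outcome measures". The next sentence reads "The test of the intervention effect will be the t-test for the regression coefficient for condition", described as an adjusted difference between conditions at posttest, two-tailed at 5%. Both statements also appear in 9.4.1 and 9.4.3. Sections 9.4.2 and 9.4.3 add "We will perform the analysis using SAS PROC GLM, Version 9.1".

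Section 9.2 says power was estimated for the paired t-test, with d = 0.43, alpha 0.05 and power 0.80, giving 136 analysed and 164 randomised. It concludes that this number "should be sufficient to detect significant differences in % weight loss across the two survey time points", and that sentence does not mention the arms.

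Section 9.4.5 adds a rule that every analysis controls for variables differing between groups at p < .10. Section 9.3 commits to intention to treat, with imputation of missing data.

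**The concern.** A paired t-test asks whether the mean of within-person differences is zero. With unmatched arms there are no pairs that link a STEPS participant to a usual-care participant, so the test cannot estimate the contrast in 9.1. Yet it is the test labelled as the main technique, for the primary endpoint and every continuous secondary endpoint.

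Two things are at stake. First, someone who follows the label would report change within arms, and change that has nothing to do with STEPS could be presented as its effect. Such change is plausible: under 8.1 both arms are weighed repeatedly and both are told to wear a Fitbit for the first week, and 6.3 says neither participants nor staff are blinded. Second, two stated tests leave the choice open until the data are in. The between-arm sentence does not fully close that gap, because it does not name the covariates behind its adjustment, and posttest could mean 3 or 6 months.

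**Working it through.** **Inputs.** d = 0.43, alpha 0.05, power 0.80, 136 analysed, 164 randomised, 20% attrition, SD 7.7% (all 9.2); 1:1 allocation (6.3); two-tailed test (9.4.2). Power is from the noncentral t distribution.

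**1. Which test gives 136?**

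- Paired test with n people: noncentrality d·√n, n − 1 degrees of freedom.
- Independent test with n per arm: noncentrality d·√(n/2), 2n − 2 degrees of freedom.

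| Test at d = 0.43, power 0.80 | Total needed |
|---|---|
| Paired, one-sided | 35 |
| Paired, two-sided | 45 |
| Independent, one-sided | 136 (68 per arm, power 0.802) |
| Independent, two-sided | 172 (86 per arm) |

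Only the independent one-sided test reproduces 136. A two-sided paired test on 136 people would have power 0.999, not 0.80. So the stated number does not come from the test that 9.2 names.

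**2. Power of the between-arm test that 9.4 describes.** Two-sided with 68 per arm: noncentrality 0.43 × √34 = 2.507 on 134 degrees of freedom, power 0.702. With 131 analysed (164 × 0.8 = 131.2, taken as 66 and 65), power is 0.685. Both figures assume no gain from covariates, because the documents give no correlation between baseline and outcome.

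**3. What a paired test within each arm would do with no true arm difference.** Suppose both arms lose the same mean m, the SD of percent loss is 7.7%, and 66 per arm are analysed (164 × 0.8 / 2 = 65.6, rounded up). Each arm's two-sided 5% test has noncentrality (m/7.7)·√66 on 65 degrees of freedom. Call its power p. The arms are independent, so the chance that STEPS is significant and usual care is not is p(1 − p).

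| Common loss m | p | p(1 − p) |
|---|---|---|
| 0% | 0.050 | 5% |
| 0.5% | 0.081 | 7% |
| 1% | 0.180 | 15% |
| 1.5% | 0.345 | 23% |
| 2% | 0.547 | 25% |
| 3% | 0.877 | 11% |
| 4% | 0.986 | 1% |

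The product cannot exceed 0.25 (at p = 0.5), so the values at 1.5% to 2% are close to the worst case. The 5% at no loss counts significance in either direction; the part in the direction of weight loss is about 2.4%.

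**The case against.** The strongest reply is that the plan already contains the right test. The sentence after the paired-test wording identifies a between-arm coefficient as the test of the intervention effect, and it is the only test given a sidedness and an error rate. PROC GLM fits it, 9.3 commits to comparing the groups as randomised, and 136 comes from a two-sample calculation. All this suggests a mislabel. That stands, and it rules out a stronger reading a reader might infer: that the trial has no valid between-arm analysis and so loses the protection of randomisation. That would follow only if the second sentence were ignored. The reply does not remove the conflict, because the paired test is called the main technique in three sections and reappears in 9.2.

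Three further inferences go too far.

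- That there is nothing to pair. Section 8.1 derives percent loss from weights at three time points, so pairing within a person is possible; it simply does not answer the question in 9.1.
- That a false claim would arise about a quarter of the time. This needs a common loss of 1.5% to 2%, which the documents do not give. The SD is also a 12-month figure from another digital programme, applied here to both arms at 6 months, and the 66 per arm are completers, whereas 9.3 would impute.
- That a paired test pooled over both arms would reject far above 5%. No section describes such a pooled test, and its rejections under a real common loss would be power against a different null hypothesis.

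**Conclusion.** The concern holds as a conflict between two stated tests. The paired t-test is wrong for the hypothesis in 9.1, and the regression coefficient for condition is a suitable test of it. How far the wrong choice could mislead depends on the unknown common loss: from about 1% to 25% over losses of 0% to 4%, under the assumptions of SD 7.7%, 66 completers per arm and no true difference. The discrepancy in 9.2 does not depend on that assumption: 136 is not a paired-test number, and the two-tailed between-arm test has power of about 0.70 with 136 analysed at d = 0.43, before any gain from covariates. This should be settled before outcomes are analysed by arm, because it decides what the primary result estimates.

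**What to change.** - **9.2 and 9.4.1 to 9.4.3:** remove the paired t-test.
- **9.4.2:** state one primary analysis, a linear model in PROC GLM of percent weight loss from baseline to 6 months on arm, with baseline weight as a prespecified covariate, two-sided 5%, reporting the adjusted arm difference and its 95% CI. Baseline weight is a recommendation; the documents do not themselves require it.
- **9.4.3:** use the same form for each continuous secondary outcome, with its own baseline value as covariate and the time point named. Report within-arm change as descriptive only.
- **9.4.5:** amend the p < .10 rule so that it cannot alter the primary model.
- **9.3:** say that the imputation is applied to this model.
- **9.2:** name the between-arm test that the sample size rests on and restate the power: about 0.70 two-sided with 136 analysed at d = 0.43, without covariate gain. Deleting the paired test alone would leave 136 with no test behind it.

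The analysis changes cost wording only, since PROC GLM is already named. Section 9.2 may cost more: for 0.80 power without covariate gain, the two-sided test needs 172 analysed, so the sponsor must either justify the lower power or a covariate gain, or revisit the number randomised.
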